12.3.5.3 Analysis of additional secondary endpoints

To support the primary endpoints, EASI50 at Week 16, EASI90 at Week 16 and the change from baseline to Week 16 in EASI score will be analysed and presented for the full analysis set. EASI50 and EASI90 will be analysed as described for the primary analysis of the primary estimand for the primary endpoints, and the change from baseline to Week 16 will be analysed as described for the primary analysis of the primary estimand for the continuous secondary endpoints.

To support the secondary endpoints on severity and extent of AD, at least 75% reduction in SCORAD score (SCORAD75) at Week 16, and SCORAD50 at Week 16 will be analysed and presented for the full analysis set. Both endpoints will be analysed as described for the primary analysis of the primary estimand for the primary endpoints.

To support the secondary endpoint on worst daily itch, the change from baseline to Week 16 in Worst Daily Pruritus NRS weekly average and the reduction of Worst Daily Pruritus NRS weekly average of at least 3 (from baseline to Week 16) will be analysed and presented for the full analysis set. The change from baseline to Week 16 in Worst Daily Pruritus NRS weekly average will be analysed as described for the primary analysis of the primary estimand for the continuous secondary endpoints. The reduction of Worst Daily Pruritus NRS weekly average of at least 3 (from baseline to Week 16) is a binary endpoint and will be analysed as described for the primary analysis of the primary estimand for the primary endpoints.

To support the secondary endpoint on HQoL, the binary endpoint reduction from baseline to Week 16 of DLQI of \geq 4 points will be analysed and presented for the subjects in the full analysis set with a baseline DLQI \geq 4 similarly to the analysis described for the primary analysis of the primary estimand for the primary endpoints.

12.3.5.4 Analysis of other endpoints

12.3.5.4.1 Efficacy over time

To further pursue the objectives supported by the five Week 16 endpoints in the confirmatory test hierarchy, these endpoints (as well as the change in Worst Daily Pruritus NRS [weekly average]) will be evaluated at each scheduled assessment up to Week 14 or each week up to Week 15:

- IGA 0/1 at each scheduled assessment until Week 14.
- EASI75 at each scheduled assessment until Week 14.
- Change in SCORAD from baseline to each scheduled assessment until Week 14.
- Change from baseline to each week through Week 1 to 15 in Worst Daily Pruritus NRS (weekly average).
- Reduction of Worst Daily Pruritus NRS (weekly average) of at least 4 from baseline to each week through Week 1 to 15.
- Change in DLQI score from baseline to each scheduled assessment until Week 14.

Nominal p-values for test of a treatment difference and 95% CI for the difference will be presented at each scheduled visit (or each week for Worst Daily Pruritus NRS) using the same approach as applied for the primary analysis of the relevant endpoint in the primary estimand.

For the binary endpoints, the same Cochran-Mantel-Haenszel test as for the Week 16 assessment will be applied. For the continuous endpoints, the repeated measurements model already described previously for the Week 16 assessments facilitates that the p-values, treatment differences and 95% CIs can be derived for each visit up to Week 14 (or Week 15 for the change in Worst Daily Pruritus NRS) in the same analysis that already will be made for the corresponding Week 16 assessments.

12.3.5.4.2 Patient-reported outcomes

The PROs POEM, DLQI, EQ-5D-5L, SF-36, WPAI-GH, HADS, and TSQM will be summarised by treatment group and visit using descriptive statistics. The summaries will be made separately for the initial treatment and the maintenance treatment. Data from the initial treatment period will be presented for the full analysis set and data from the maintenance treatment period will be presented for the maintenance analysis set.

The PROs collected in the eDiaries on a daily basis (Worst Daily Pruritus NRS, Average Daily Pruritus NRS, Eczema-related Sleep NRS, PGI-B, and PGI-S) will all be summarised over time by treatment group using descriptive statistics. The summaries will be separate for the initial treatment and the maintenance treatment. Data from the initial treatment period will be presented for the full analysis set and data from the maintenance treatment period will be presented for the maintenance analysis set.

Trial ID: LP0162-1325	Date: 14-Aug-2018	Version: 4.0
		Page 107 of 169

The Average Daily Pruritus NRS collected over the last week prior to baseline will be used to calculate the baseline average daily itch. A minimum of 4 Average Daily Pruritus NRS scores out of the 7 days is required to calculate the baseline average score.

To investigate a possible early onset of itch relief, a reduction in Worst Daily Pruritus NRS weekly average of at least 3 from baseline to Week 2 will be summarised by treatment group and analysed as described for the primary analysis of the primary estimand for the primary endpoints.

In the subgroup of subjects with either HADS anxiety subscale score ≥ 8 or HADS depression subscale score ≥ 8 at baseline, the proportion of subjects with both HADS anxiety subscale score <8 and HADS depression subscale score <8 at Week 16 will be summarised by treatment group and analysed as described for the primary analysis of the primary estimand for the primary endpoints.

In the subgroup of subjects with a baseline POEM score of at least 4, the proportion of subjects with a reduction in POEM score of at least 4 at Week 16 will be summarised by treatment group and analysed as described for the primary analysis of the primary estimand for the primary endpoints.

The change from baseline to Week 16 in Eczema-related Sleep NRS weekly average, HADS, POEM, SF-36, WPAI-GH, and the EQ-5D-5L index will be summarised by treatment group and domain, where applicable, and analysed as described above for the primary analysis of the primary estimand of the continuous secondary endpoints. For the Eczema-related Sleep NRS score, the mean over the last 7 days prior to randomisation will be used as the baseline value.

The treatment satisfaction (TSQM) at Week 16 will be summarised by treatment group and domain and compared between treatments using an analysis of variance model including treatment, region and baseline IGA as factors.

For the PGI-B, a day of 'no or slight bother' is defined as answering the question with 'not at all' or 'slightly'. The subjects' number of days of 'no or slight bother' will be tabulated per treatment group for the initial treatment period. The mean number of days will be presented with 95% CIs and compared between the 2 treatment groups using an analysis of variance model including treatment, region, and baseline IGA as factors. In this analysis, data collected after permanent discontinuation of IMP or after initiation of rescue medication will be disregarded.

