- 9) The eDiary consists of (i) Eczema-related Sleep NRS, (ii) Worst Daily Pruritus NRS, (iii) Average Daily Pruritus NRS, (iv) PGI-B, and (v) PGI-S. The eDiary will be completed daily from Week -2 to Week 52.
- 10) IgE not assessed at screening.
- 11) Optional, selected trial sites only.
- 12) At baseline, a total of 4 skin biopsies will be taken (2 from lesional skin, 2 from non-lesional skin) at an anatomically similar site.

ADA, anti-drug antibodies; Bcg, background; BSA, body surface area; C-SSRS, Columbia-Suicide Severity Rating Scale; DLQI, Dermatology Life Quality Index; EASI, Eczema Area and Severity Index; EASI75, at least 75% reduction in EASI score; ECG, electrocardiogram; eDiary, electronic diary; EQ-5D-5L, EuroQoL 5-Dimension Health Questionnaire 5 Level; HADS, Hospital Anxiety and Depression Scale; IGA, Investigator's Global Assessment; IgE, immunoglobulin E; IMP, investigational medicinal product; NA, not applicable; NRS, numeric rating scale; PGI-B, Patient Global Impression of Bother; PGI-S, Patient Global Impression of Severity; POEM, Patient Oriented Eczema Measure; Q2W, every 2 weeks; SCORAD, Scoring Atopic Dermatitis; SF-36, 36-Item Short Form Health Survey; TSQM, Treatment Satisfaction Questionnaire for Medication; WPAI-GH, Work Productivity and Activity Impairment – General Health.

Trial ID: LP0162-1325	Date: 14-Aug-2018	Version: 4.0
		Page 22 of 169

Panel 3 Schedule of trial procedures: maintenance treatment period and follow-up

							N	Iainten	ance tı	eatmei	nt perio	bd							FU1 ²
Visit	13	14	15	16	17	18	19	20	21	22	23	24	25	26	27	28	29	30 ¹	31
Week	18	20	22	24	26	28	30	32	34	36	38	40	42	44	46	48	50	52	66
Visit window (days)	±3	±3	±3	±3	±3	±3	±3	±3	±3	±3	±3	±3	±3	±3	±3	±3	±3	±3	±3
Trial products (Section 9)																			
IMP administration and compliance	Х	X	Х	Х	Х	Х	Х	X	Х	Х	X	Х	Х	X	Х	Х	Х		
Concomitant medication/procedures	х	х	х	х	х	Х	х	x	х	х	x	х	х	x	Х	Х	х	х	х
Investigator assessments of efficacy (Sect	Investigator assessments of efficacy (Section 10.3.1)																		
IGA	X ³	X ³	X ³	X ³	X ³	X ³	X ³	X ³	X ³	X ³	X ³	X ³	X ³	X ³	X ³	X ³	X ³	Х	
EASI	X ³	X ³	X ³	X ³	X ³	X ³	X ³	X ³	X ³	X ³	X ³	X ³	X ³	X ³	X ³	X ³	X ³	х	
SCORAD		х		х		х		х		х		х		x		Х		х	
Subject assessments of efficacy (Section 1	10.3.2)																		
eDiary ⁴		<-==															>		
POEM and DLQI		х				Х				Х				x				Х	
EQ-5D-5L and HADS		х				х				х				x				х	
SF-36 and WPAI-GH		Х				Х				Х				X				Х	
TSQM				Х														х	

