7.1 Overall trial design

Overview

This is a phase 3 randomised, double-blinded, placebo-controlled trial in adult subjects with moderate-to-severe AD. The trial will consist of a screening period of 2 to 6 weeks (Weeks -6/-2 to 0), an initial treatment period of 16 weeks (Weeks 0 to 16) and a maintenance treatment period of 36 weeks (Weeks 16 to 52). The primary endpoint is assessed at Week 16, and the final efficacy assessment will be conducted at Week 52. A 14-week off-treatment follow-up period for the assessment of safety is also included (Weeks 52 to 66). Subjects not achieving a clinical response at Week 16 as well as those who meet certain criteria during maintenance treatment will be transferred to open-label tralokinumab 300 mg Q2W treatment with optional use of TCS up to Week 52. An overview of the different parts of the trial is provided in Panel 1 and Panel 9.

Screening period (Week -6 to Week 0)

The screening period has a minimum duration of 2 weeks and a maximum duration of 6 weeks and includes 1 or 2 screening visits. The exact duration of the screening period depends on the washout period defined by the exclusion criteria (Section 8.3). If a washout is not required, screening will be reduced to 2 weeks and only requires 1 visit (Week -2; visit 2), i.e., the 2 screening visits will be merged. Similarly, if only a 2-week wash-out is required, screening visits 1 and 2 will be combined (Week -2; visit 2). Eligibility will be assessed at the (first) screening visit and on Day 0 prior to randomisation.

All subjects will attend a screening visit 14 days before baseline (Week -2; visit 2) where they will receive electronic diary (eDiary) training and start the eDiary. Data entered in the eDiary during the 2 weeks before randomisation will be used to calculate baseline values of the patient-reported outcomes (PROs).

All subjects will use an emollient twice daily (or more, as needed) for at least 14 days before randomisation and will continue this treatment throughout the trial. Subjects will initiate emollient treatment no later than the Week -2 visit.

Trial ID: LP0162-1325	Date: 14-Aug-2018	Version: 4.0
		Page 41 of 169

Initial treatment period (Week 0 to Week 16)

Following the screening period, approximately 780 subjects will be randomised 3:1 to one of the following groups stratified by region and disease severity (IGA of 3 or 4)

- Tralokinumab 600 mg (4 mL) at Day 0 (hereinafter "baseline"), then 300 mg (2 mL) Q2W.

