10.3.2.4 Patient Global Impression of Bother

The Patient Global Impression of Bother (PGI-B) is a single item designed to capture the subject's perception of how bothered they have been by their AD over the past 24 hours at the time of completion. A 5-point categorical response scale will be used ('not at all', 'slightly', 'somewhat', 'a lot', 'very much'). Subjects will complete this item as part of the eDiary each day in the morning from Week -2 (visit 2) until Week 52. The PGI-B is included in the investigator trial file.

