12.3.5.2.1 Primary estimand for the continuous secondary endpoints: 'hypothetical'

The primary estimand for the continuous secondary endpoints will be:

• Treatment difference in change from baseline to Week 16 in SCORAD and DLQI, respectively, if all subjects adhered to the treatment regimen in the sense that they did not discontinue IMP permanently and no rescue medication was made available before Week 16.

The primary estimand assesses the expected benefit when adhering to the treatment regimen tralokinumab with no rescue medication as compared to a treatment regimen with placebo with no rescue medication.

Primary analysis of the primary estimand (continuous secondary endpoints)

Data collected after permanent discontinuation of IMP or after initiation of rescue medication will not be included in the analysis.

The endpoints will be analysed using a repeated measurements model on the post baseline responses up to Week 16 with an unstructured covariance matrix, Kenward-Roger approximation to estimate denominator degrees of freedom, and the mean modelled as follows (shown for change from baseline in SCORAD):

Change from baseline in SCORAD

= treatment \times visit + baseline SCORAD \times visit + region + baseline IGA

This model assumes that data is missing at random within each treatment arm. The estimates will be presented with nominal p-values and 95% CI at each visit. The primary comparison between tralokinumab and placebo will be at Week 16.

Sensitivity analysis for the primary estimand (continuous secondary endpoints)

Rather than assuming that observations are missing at random within each treatment arm it is assumed that missing data from subjects who discontinue treatment/receive rescue medication in the tralokinumab arm will resemble data from subjects from the placebo arm who do not discontinue treatment/receive rescue medication. Imputation of missing data at Week 16 will be done using a pattern mixture model where missing data in the tralokinumab arm as well as the placebo arm will be imputed from the placebo arm (using a so-called copy-reference approach). The procedure for the change from baseline in SCORAD at Week 16 is described below. The same procedure will be applied for the DLQI endpoint.

1. Intermittent missing values will be imputed in each group using a Markov Chain Monte Carlo method to obtain a monotone missing data pattern and 100 copies of the dataset will be generated (seed=29099725).

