12.3.10 General principles

Unless otherwise stated, all significance tests will be two-sided using the 5% significance level. All CIs will be presented with 95% degree of confidence.

An observed-cases approach will be used for tabulations of data by visit (i.e. involving only those subjects who attended each specific visit).

Trial ID: LP0162-1325	Date: 14-Aug-2018	Version: 4.0
		Page 114 of 169

Categorical data will be summarised using the number and percentage of subjects in each category and treatment group. Continuous data will be summarised using the mean, median, standard deviation, minimum and maximum values.

All the analyses specified in the protocol will be reviewed in relation to the blinded data actually obtained and the statistical analysis plan update will be finalised before breaking the randomisation code.

Any changes from the statistical analysis planned in this clinical trial protocol will be described and justified in a protocol amendment, the statistical analysis plan update and/or in the CTR dependent on the type of deviation.

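### The comparison of PGI-B days of 'no or slight bother' omits baseline PGI-B as a covariate, which probably costs a little precision

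*Protocol*

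**What the plan says.** Protocol section 12.3.5.4.2 defines a good day as one on which the PGI-B answer falls in either of the two mildest of its five categories. It then states: "The subjects' number of days of 'no or slight bother' will be tabulated per treatment group for the initial treatment period". The mean counts are "compared between the 2 treatment groups using an analysis of variance model including treatment, region, and baseline IGA as factors". Diary data after permanent discontinuation of IMP or after the start of rescue medication are set aside.

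Section 10.3.2.4 has subjects answer the PGI-B as "part of the eDiary each day in the morning from Week -2 (visit 2) until Week 52". Panel 2, footnote 9, agrees: "The eDiary will be completed daily from Week -2 to Week 52". Section 7.1 says that diary entries from the two weeks before randomisation will supply the baseline values of the patient-reported outcomes.

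In the same part of the protocol, the change scores (Eczema-related Sleep NRS, HADS, POEM, SF-36, WPAI-GH and the EQ-5D-5L index) use the repeated measurements model of section 12.3.5.2.1. That model includes the outcome's own baseline, crossed with visit, besides region and baseline IGA. TSQM is compared with the same ANOVA as the PGI-B days.

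SAP section 6.6 refers back to the protocol for efficacy. Its paragraph on PGI-B and PGI-S (section 6.6.5) treats both items as non-numerical and shows the worst score of each week rather than a weekly mean. It adds no covariate to the comparison of days.

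**The concern.** Subjects differ in how readily they call themselves bothered. Some of that difference is visible before treatment starts, in answers to the same question in the same diary. If it predicts the later day count, leaving it out of the model keeps explainable variation in the error term and widens the interval for the treatment difference. Baseline IGA is an investigator rating in two categories and is unlikely to carry all of that information.

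The plan gives no reason for the omission. TSQM has an evident one: Panel 2 schedules it at Weeks 2 and 16 only, so it has no baseline. PGI-B does have one. Amendment 2 revised the handling of PGI-B data after discontinuation or rescue to match the primary estimand for the continuous secondary endpoints, but left the covariates different from that model.

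At stake is the width of one confidence interval, not the validity of the comparison.

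**Working it through.** **The plan's own figure.** The documents give no standard deviation, power or interval width for PGI-B days, so there is nothing to reproduce for this analysis. The power statements in protocol section 12.1 do reproduce (IGA 0/1, 30% against 10%, 585 and 195 subjects, two-sided 5%: power above 0.9999, against a stated value above 99%), but they have no bearing on PGI-B.

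**Inputs**
- Planned arms of 585 and 195, 780 in total (protocol 12.1).
- Confidence level (protocol 12.3.10): "All CIs will be presented with 95% degree of confidence".
- Residual degrees of freedom of the planned ANOVA: 780 - 1 (intercept) - 1 (treatment) - 2 (region, three levels) - 1 (IGA 3 or 4) = 775. One more covariate leaves 774.
- r, the partial correlation of baseline PGI-B with the day count given treatment, region and baseline IGA. This is an assumption, shown as a range. Its sign is irrelevant.

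**Current precision.** In units of the residual SD, the standard error of the treatment difference is sqrt(1/585 + 1/195) = 0.0827. The 95% half-width is 1.96 x 0.0827 = 0.162 SD.

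**Effect of the covariate.** Residual variance is multiplied by 1 - r^2 and interval width by sqrt(1 - r^2). The extra term costs a degree of freedom and allows for chance imbalance: sqrt(775/774) x sqrt(1 + 1/772) = 1.0013. The change in the t quantile is negligible.

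| Assumed r | sqrt(1 - r^2) | times 1.0013 | Change in CI width | Half-width in SD, before the 1.0013 factor |
|---|---|---|---|---|
| 0 | 1.0000 | 1.0013 | 0.13% wider | 0.162 |
| 0.05 | 0.9987 | 1.0000 | none | 0.162 |
| 0.1 | 0.9950 | 0.9963 | 0.4% narrower | 0.161 |
| 0.2 | 0.9798 | 0.9811 | 1.9% narrower | 0.159 |
| 0.3 | 0.9539 | 0.9552 | 4.5% narrower | 0.155 |
| 0.4 | 0.9165 | 0.9177 | 8.2% narrower | 0.149 |
| 0.5 | 0.8660 | 0.8672 | 13.3% narrower | 0.140 |

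Put as sample size, the unadjusted analysis would need about 780/(1 - 0.09) = 857 subjects to match the adjusted one at r = 0.3, and 780/(1 - 0.16) = 929 at r = 0.4.

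**Which form of baseline.** Entry requires IGA of at least 3 and average worst itch of at least 4 (protocol 8.2), so few baseline days are likely to count as good days. An illustrative simulation with invented inputs used 14 baseline days, about 2% to 8% of them good, and partial correlations of about 0.15 to 0.54 in absolute size. The mean baseline score narrowed the interval by about 1% to 16%, and a count of good baseline days by only 0.4% to 9%. This supports the mean score over the count; it does not predict the gain in this trial.

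**Cost of dropping subjects.** If a fraction f lacks a usable baseline and is dropped evenly, width grows by 1/sqrt(1 - f). That cancels the gain when f is about r^2: 4% of subjects at r = 0.2, 9% at r = 0.3.

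**The case against.** The strongest reply is that this is a preference about efficiency, not an error. Randomisation is stratified by region and baseline IGA, and both are in the model. PGI-B days is not a Panel 6 endpoint and appears in neither the protocol's testing hierarchy nor the US hierarchy of SAP section 6.6.1. It is a count over a period, not a change score, so the change-from-baseline analyses are an imperfect comparator, and the model matches TSQM, the other outcome here that is not a change score. All of this stands, and it sets the importance of the point. It does not remove the point: TSQM has no baseline to adjust for, and PGI-B has.

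Three stronger readings are tempting and not supported.
- A reader might infer that the comparison is biased or its interval invalid. Under randomisation the omission affects precision only.
- A reader might infer that the pre-randomisation PGI-B entries go unused. Section 7.1 assigns the diary run-in to baseline values, and section 12.3.5.4.2 summarises PGI-B over time. The entries are only absent from this model.
- A reader might take r^2 (4%, 9% and 16% at r = 0.2, 0.3 and 0.4) as the gain in interval width. Those are variance reductions, and r must be the partial correlation, because baseline IGA may already carry part of the information.

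The objection that a mean PGI-B score sits awkwardly with the SAP's description of the item as non-numerical also stands, and the fix has to deal with it. Finally, the plan gives no denominator of observed days once days after discontinuation or rescue are set aside. That may matter more for this endpoint, but it is a separate question, and the covariate does not answer it.

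**Conclusion.** The point holds as a minor, optional improvement. The model leaves out a baseline measure of the same item that the trial already collects, and neither document explains why. The likely cost is an interval somewhat wider than necessary: about 2%, 4.5% and 8% for assumed partial correlations of 0.2, 0.3 and 0.4. There is no gain below about |r| = 0.05, and the worst case, r = 0, is 0.13% wider. A partial correlation above 0.05 is very likely for the same daily question in the same subject, but that is a judgement; the documents give neither r nor the SD of the day count. The figures also assume the planned 780 subjects, all with a usable baseline. No confirmatory conclusion depends on this analysis.

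**What to change.** Before unblinding, add one baseline PGI-B covariate to this model, making it an ANCOVA. A workable definition scores the five ordered categories 0 to 4 and takes the mean over the 7 days up to and including randomisation, requiring at least 4 entries. This mirrors the rule for Worst Daily Pruritus in inclusion criterion 9 and SAP section 6.6.5. The rule must be written out, because the SAP default (section 6.8.1) would take only the latest pre-dose entry.

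State that the scoring serves the covariate only. The endpoint, the weekly worst-score presentation and the SAP's treatment of PGI-B as non-numerical then stay as they are.

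The cost is one model term plus a scoring, window and completeness rule. Subjects with too few baseline entries would be dropped, or kept by imputing the overall baseline mean. Few are expected, since eligibility already requires 4 of 7 entries for the pruritus item in the same diary, but the documents set no such rule for PGI-B. Keeping them avoids giving back the gain. Protocol section 12.3.10 allows the change through a SAP update; after unblinding it should be added only as a labelled supplementary analysis.

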	 The description of the analysis of the following 2 endpoints have been removed from this section: Reduction of at least 4 from baseline to Week 2 in Worst Daily Pruritus NRS weekly average Change from baseline to Week 2 in Worst Daily Pruritus NRS weekly average. 	The analysis of these endpoints is now covered by the new section 12.3.5.4.1.
	For the PGI-B, a day of 'no or slight bother' is defined as answering the question with 'not at all' or 'slightly'. The subjects' number of days of 'no or slight bother' will be tabulated per treatment group for the initial treatment period. The mean number of days will be presented with 95% CIs and compared between the 2 treatment groups using an analysis of variance model including treatment, region, and baseline IGA as factors. In this analysis,	Clarification regarding data collected after permanent discontinuation of IMP or after initiation of rescue medication, to align with the primary estimand for the continuous secondary endpoints.
	data collected after permanent discontinuation of IMP or after initiation of rescue medication will be disregarded.	

Section number and name	Description of change	Brief rationale
Section 12.3.6.1 Analysis of maintenance endpoints	 The main changes are as follows: An estimand framework has been introduced for the analysis of the maintenance endpoints. The primary analysis provided in the statistical analysis plan in the original protocol dated 03-Mar-2017 is unchanged. Clarification has been added on the analysis set for the maintenance endpoints IGA of 0/1 at Week 52 and EASI75 at Week 52. The sensitivity analysis allowing TCS treatment under certain conditions has been removed (mild to moderate strengths [WHO classification] TCS, on ≤250 cm2 affected BSA, for ≤5 consecutive days, not more often than every 4 weeks, ≤3 courses from Week 16 to Week 50 and last course is completed prior to the Week 50 visit, allowing at least a 2-week washout prior to the Week 52 assessment). An LOCF sensitivity analysis has been introduced. 	To conduct a sensitivity analysis which is similar to the sensitivity analysis no. 2 for the primary estimand for the primary endpoints. The sensitivity analysis described in the original protocol – which allowed TCS under certain conditions – is inconsistent with the rescue medication algorithm applied in the initial treatment period.

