#### Calculation of Weekly average of pruritus NRS

The weekly average will only be calculated if at least 4 assessment are available. When calculating the baseline value for the weekly average of Worst Daily Pruritus, the daily assessments in the 7 days preceding the randomisation will be used, including the day of randomisation.

For the initial treatment period, the NRS weekly average for Week 1 will be calculated based on scores recorded on day 1 to day 7 (where day 0 is the day of the first dose). Similarly, for Weeks 2 to Week 15, the weekly average for Week x will be calculated based on scores recorded on day 7\*x-6 to day 7\*x (where day 0 is the day of first dose). To account for the actual day maintenance or open-label treatment is initiated, the Week 16 weekly average will instead be based on the last 7 days before (and including) the day of the Week 16 visit, thus

Trial ID: LP0162-1325	Date: 20-May-2019	Version: 1.0
		Page 19 of 31

ensuring that the Week 16 weekly average is based on data from the initial treatment phase only, and also ensuring alignment in timing with other Week 16 efficacy endpoints. Also, for the calculation of Week 1 to Week 15 weekly averages, any scores recorded after the Week 16 visit date will be disregarded (only relevant if Week 16 visit is out of window).

For Week 17 of the maintenance treatment period, the weekly average will be based on the first 7 days after (not including) the Week 16 visit. For Week 18 to Week 52 of the maintenance treatment period, the weekly average for Week x will be calculated based on scores recorded on day 7\*x-6 to day 7\*x (where day 0 is the day of the first dose). Any scores recorded after initiation of open-label treatment will be disregarded.

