#### PGI-B and PGI-S

For the PGI-B and PGI-S, which are not numerical, the worst score recorded during the week will be presented instead of weekly averages. The worst score will be derived if at least one measurement is available for the week in question. The same rules regarding visit windowing apply as for weekly average pruritus NRS described above. The daily scores will be presented graphically.

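### The PGI-B day count has no denominator, so diary days removed after rescue or discontinuation score as days with bother, which is not the hypothetical estimand the exclusion was meant to match

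*Protocol*

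**What the plan says.** Protocol section 12.3.5.4.2 calls a diary day one of 'no or slight bother' when the subject answers in either of the two mildest categories of PGI-B. Each subject's number of such days in the initial treatment period is tabulated. The mean number is "compared between the 2 treatment groups using an analysis of variance model including treatment, region, and baseline IGA as factors". The section then states: "In this analysis, data collected after permanent discontinuation of IMP or after initiation of rescue medication will be disregarded".

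The Amendment 2 entry in Appendix 10 gives the reason for that sentence, which is still in force. It describes a clarification about "data collected after permanent discontinuation of IMP or after initiation of rescue medication, to align with the primary estimand for the continuous secondary endpoints". Section 12.3.5.2.1 defines that estimand as hypothetical: no permanent discontinuation and no rescue before Week 16. It is estimated with a repeated measurements model, and "This model assumes that data is missing at random within each treatment arm".

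In the same PRO section, another daily diary score, the Eczema-related Sleep NRS, is "analysed as described above for the primary analysis of the primary estimand of the continuous secondary endpoints".

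The SAP leaves the count unchanged. Its PGI-B text in section 6.6.5 covers a weekly worst score and plots of daily scores: "The worst score will be derived if at least one measurement is available for the week in question" and "The same rules regarding visit windowing apply as for weekly average pruritus NRS described above". On missing data, protocol section 12.3.11 refers to the individual analysis sections and SAP section 6.8.7 refers back to the protocol. Section 12.3.5.4.2 has no missing-data rule for the PGI-B count.

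**The concern.** In a repeated measurements model, a disregarded visit is treated as missing, and the model assigns it no bad value. In a raw count, a disregarded day contributes zero, and so does a day with bother. PGI-B therefore takes over the data exclusion of the hypothetical estimand without the model that makes the exclusion neutral. Ordinary missed diary entries are scored in the same way.

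Subjects on topical rescue stay on IMP (protocol section 9.7) and the diary is daily. A day actually reported as free of bother after topical rescue therefore also adds nothing.

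At stake is the reading of one nominal p-value and confidence interval. A reader who takes the result as hypothetical would see a difference that partly reflects how often, and how early, subjects in each arm were rescued or stopped.

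**Working it through.** The plan states no figure for this analysis, so there is none to reproduce.

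**Inputs from the documents.** The period is 16 weeks, or 112 days. Planned arms are 585 and 195 (protocol section 12.1). Tests are two-sided at 5% (section 12.3.10).

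**Assumed inputs.** The documents give no rescue or discontinuation rates and no frequency of good days.
- r = share of an arm truncated by rescue or discontinuation.
- q = chance that a day is one of no or slight bother, constant over time and unrelated to truncation.
- Truncation is spread evenly over days 14 to 98, so the mean number of days lost is 112 − (14 + 98)/2 = 56.

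**One subject.** With q = 0.5 and rescue on day 28, the expected count is 0.5 × 28 = 14. Without rescue it is 0.5 × 112 = 56. The 84 removed days enter exactly as 84 days with bother. The proportion of observed days is 0.5 either way.

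**Two arms.** The expected count in an arm is 112q − 56rq. The hypothetical difference is 112(qT − qP). The bias of the raw count is therefore

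56 × (rP·qP − rT·qT),

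which is zero only when qT/qP = rP/rT.

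| qT vs qP | rT vs rP | True difference (days) | Bias (days) | Count shows |
|---|---|---|---|---|
| 0.30 vs 0.30 | 20% vs 20% | 0 | 56 × (0.06 − 0.06) = 0 | 0 |
| 0.30 vs 0.30 | 20% vs 30% | 0 | 56 × (0.09 − 0.06) = +1.7 | +1.7 |
| 0.30 vs 0.30 | 20% vs 40% | 0 | 56 × (0.12 − 0.06) = +3.4 | +3.4 |
| 0.50 vs 0.15 | 20% vs 40% | 39.2 | 56 × (0.06 − 0.10) = −2.2 | 37.0 |
| 0.50 vs 0.30 | 20% vs 20% | 22.4 | 56 × (0.06 − 0.10) = −2.2 | 20.2 |
| 0.50 vs 0.30 | 20% vs 30% | 22.4 | 56 × (0.09 − 0.10) = −0.6 | 21.8 |
| 0.50 vs 0.30 | 20% vs 40% | 22.4 | 56 × (0.12 − 0.10) = +1.1 | 23.5 |
| 0.40 vs 0.30 | 20% vs 40% | 11.2 | 56 × (0.12 − 0.08) = +2.2 | 13.4 |

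Positive bias favours tralokinumab. Equal truncation is harmless only when there is no effect; with a true benefit it shrinks the difference.

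**Simulation with 585 vs 195 subjects and no effect (q = 0.30).** The raw count is biased by −0.01, +1.63 and +3.29 days at 20/20, 20/30 and 20/40% truncated, in line with the formula. The rejection rate depends on the assumed between-subject SD on the logit scale:
- 20% vs 40%: 50% at SD 1.0, falling to 22% at SD 2.5.
- 20% vs 30%: 19% at SD 1.0, falling to 9% at SD 2.5.
- 20% vs 20% (SD 1.5): 3.4%.
- 20% vs 40% (SD 1.5) with truncation concentrated in subjects with few good days: 15% to 19%.

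A simpler beta-binomial model with event times uniform over the 112 days gives 11% at 20% vs 30% and 29% at 20% vs 40% for the raw count. The proportion of days before the event gives 4.5% to 5.8%.

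**The alternative.** A weekly proportion of observed good days in a repeated measurements model has bias of at most 0.25 days across the nine SD 1.5 scenarios. Rejection is 2.8% to 6.2% in the five of these with no effect (Monte Carlo error about 2 points). Requiring one diary entry per week instead of four does not change this. In all runs each subject had at least 14 diary days, and strong not-at-random truncation was not tested.

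**The case against.** Section 12.3.5.4.2 names no estimand for PGI-B. The link to the hypothetical one is a rationale cell in the amendment history, and that cell speaks only of which data are used. In that narrow sense the exclusion does align. The cell does, however, give the purpose of wording still in force, so citing it does not set superseded text against current text. Removing the same data does not produce the same estimand when the summary is an unscaled sum.

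The count could also be called a total while on treatment and before rescue, rather than a composite. That is fair as to the label, but under neither label is it hypothetical.

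The no-effect scenarios pair equal daily bother with 1.5 to 2 times as much truncation on placebo. Since rescue is for intolerable symptoms, that pairing is hard to explain in a blinded trial. This weakens the rejection rates as a forecast, and they should be read as illustrations. In the larger-benefit rows of the table the distortion is at most 10% of the effect (2.2 of 22.4 days). With the 11.2-day effect it reaches 2.2/11.2, or 20%.

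The plan also summarises daily PGI-B over time by arm, and the SAP adds weekly worst scores and plots. These give context but do not supply the missing denominator.

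Finally, a repeated measurements model is a lot of machinery for one nominal comparison, and it rests on missing at random. Both points stand, which is why relabelling is an acceptable minimum.

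**Conclusion.** The concern holds. As written, the PGI-B comparison estimates rescue-free, on-treatment good days, not the difference that would be seen without rescue or discontinuation. Relative to the hypothetical target it is biased whenever the good days lost differ between arms, and the bias can go either way. Across the assumed scenarios it ranges from −2.2 to +3.4 days. The true size is unknown because the documents give no event rates by arm.

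This is a minor point. PGI-B is not listed in Panel 6 and the comparison lies outside the testing hierarchy, so no confirmatory claim changes. The count is a coherent summary if a composite is what the sponsor wants, but it must then be labelled as one.

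**What to change.** Preferred: analyse the weekly proportion of observed diary days with no or slight bother, up to rescue or discontinuation. Use a repeated measurements model of the section 12.3.5.2.1 type, with treatment by week, baseline by week, region and baseline IGA. The weekly windows that the SAP already applies to PGI-B can be used. The SAP should also state:

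- The minimum number of diary entries per week for this variable. The pruritus rule is one option ("The weekly average will only be calculated if at least 4 assessment are available"); the PGI-B worst score needs only one entry.
- The PGI-B baseline window. Protocol section 7.1 refers to two weeks of diary data, while section 12.3.5.4.2 uses 7 days for the Sleep NRS. The raw count needs no baseline, so this question arises only with the new model.
- The handling of subjects with no usable post-baseline week. SAP section 6.6.3 carries the baseline value forward for the continuous secondary endpoints.

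Report the average weekly difference, multiplied by 112 for a figure in days, and the observed diary days per arm. Under the assumptions above at 20% vs 40% truncated, these would be 112 − 56 × 0.2 = 100.8 and 112 − 56 × 0.4 = 89.6.

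Minimum: keep the count, label it a composite, present it as supportive and report observed diary days per arm.

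The preferred change costs one derived variable, one model and some SAP wording, with no new data. It relies on data missing at random within arm, as the SCORAD and DLQI analyses already do.
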